1.4.1 Preliminary Data 1: We conducted a randomized, double blind, placebo-controlled laboratory study examining the gender effects of 3-weeks Guanfacine immediate release (GUA 2 to 3mgs; b.i.d) using a 12 day titration schedule in a sample of early abstinent treatment-seeking alcohol dependent men and women (N=24; 8F/16M). Method: Following 3-weeks of abstinence, all participants were exposed to three, 10-min personalized guided imagery scenarios (i) stress, ii) cue, iii) combined stress/cue), one per day, across 3 consecutive days in a random, counterbalanced order. Alcohol craving, nicotine craving, anxiety, negative mood, cardiovascular, HPA and sympathetic measures were acquired at baseline, immediately following imagery, and at various recovery time-points until 1 hour post imagery. Results: GUA was found to be safe and well tolerated in both men and women, with fatigue being the most commonly reported side-effect. All symptoms were reported as being mild to moderate and dissipated within the initial two weeks of inpatient stay. At baseline, GUA reduced cardiovascular output in women compared with both PLA groups ($p<.0001$, in all cases). Following imagery exposure, a series of Medication Group X Gender X Time-point interactions showed that immediately following all 3 imageries the GUA females reported significantly attenuated anxiety [$F5, 644 = 2.8, p<.02$], sadness [$F5, 644 = 2.4, p<.04$], arousal [$F5, 644 = 3.7, p=.003$] behavioral arousal (sweaty palms, crying) [$F1, 30 = 3.6, p=0.06$] as well as increased positive mood [relaxed state: $F5, 644 = 2.7, p<.02$; Joy: $F5, 644 = 2.8 p<.02$] compared with the PLA females (Fig 1). Importantly these attenuations in stress reactivity occurred alongside decreased alcohol craving across all conditions in the GUA females compared with the PLA females [$F5, 644 = 2.7, p=.02$]. No such discrepancy was observed between GUA and PLA males, with the exception of nicotine craving and SBP which was attenuated in both the male and female GUA groups. Findings support preclinical studies showing attenuation of alcohol-seeking, relapse and other negative reinforcing aspects of alcohol craving following alpha2 agonism.

Fig. 1 Response to stress-, cue- & combined stress & cue-related imagery: GUA vs PLA in alcoholic men & women

[figure not shown]

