Subjects will initially be screened over the phone. They will then be emailed the consent form to read and scheduled for a consent appointment over zoom, where they will be taken through the consent procedure with a research coordinator and given time to ask questions. Consent will be proved using Docu-sign. Participants will then be scheduled for an appointment at the CRC where they will provide a baseline blood draw, HCG urine test and urine toxicology. An EKG test will also be performed. If a stay at home order is in place, subjects will be required to provide a current EKG (within the last three months) as well as the last blood pressure reading from their most recent primary care physician visit. If they are unable to provide this, they will be waitlisted until they are able attend the CRC. All questionnaires and clinical interviews (including the SCID) will be performed over ZOOM by virtual visit. All clinical testing will be reviewed by the study physician ([name]).

If the subject proves to be in good health (as confirmed with the study physician) and meets study inclusion / exclusion criteria, a package will be sent out in the mail by UPS. The package will contain a blood pressure monitor kit, urine toxicology cups, disposable breathalyzers for alcohol and 1 week of medication (dose determined by week in study)

timeline calendar, blood pressure heart rate daily log, and written instructions on how to perform these tests.

INTAKE 2: Intake 2 will be conducted early in the morning in order to ensure that the initial medication dose is as close to 8am as possible.

Once the package is received by the participant, the second intake will be performed over virtual media (ZOOM). The subject will first meet briefly with the study physician in order to establish good health. The subject will then meet with the study RA to complete questionnaires, the timeline follow back and take a tutorial on how to use the blood pressure monitor. All subjects will also provide a urine sample to assess drug use by taking a photo of the test strip on the urine cup using their cell phone, and sending it to the study site cell phone to be printed and stored in the participant binder.

Disposable breathalyzer tests will additionally be completed and logged in the participant binder and results displayed via zoom.

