Participant will then administer the first dose of study medication or virtual media visit. Questionnaires and surveys will be conducted and timeline follow back will be obtained. Sit stand blood pressure recordings will be taken at the end of this intake. Appointment for the weekly virtual visits will be scheduled.

Medication

At a second intake appointment participants will meet with the study MD, and once cleared begin the first dose of Guanfacine or placebo. They will be randomly assigned to either GXR (3mgs) or PLA, and will receive the exact amount of medication until their next visit, provided in unit/dose containers and labeled with the time and date to facilitate appropriate dosing. Riboflavin will be added to the medications and blood plasma assessed for medication levels every four weeks to ensure compliance¹³¹. The use of extended release GXR will also necessitate the use of only 1 tablet per day, increasing likelihood of adherence

ALL SESSIONS:

SAFETY GUIDELINES FOR THE COVID-19 VIRUS DURING:

WEEKLY STUDY VISITS 2 x per week – all virtual:

All assessments will be performed by virtual visit over a secured media site. Using ZOOM with end to end encryption. Subjects will be mailed via UPS with signature required: 1 BP monitoring kit, Urine toxicology cups, 1-week medication until titrations to the optimal dose of 3 mg of Guanfacine or Placebo; based on the blind randomization assigned by the pharmacist. Subjects will receive virtual tutorials from the research staff on the use of the BP monitor and utilization of the urine toxicology cups through zoom. Subjects will be monitored via virtual media during the use of these tools each visit. All adverse events to be reported and documented during these visits. Reported to study MD as needed and virtual visit with MD as needed. All SAFTEE documents will be administered and documented. One virtual visit each week will include medication management, with continued assessment of the subject during the COVID_19 crisis to insure that additional counseling is not needed.

Weekly Assessments include the following:

1. SAFTEE sheet – documenting any adverse effects

2. A series of short rating scales measuring: craving (AUQ), stress (PSS), emotion regulation (DERS), mood (POMS), anxiety (STAXI), depressive symptoms (BDI) and withdrawal symptoms (CIWA)
3. Timeline follow back (TLFB) – subject report of daily alcohol/drug use
3. Vitals – sitting to standing

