Medical management (MM) & contingency management (CM) for treatment adherence: The primary focus of the MM protocol¹³⁴ is to assist clinicians in providing educational support strategies for maintaining medication adherence. It was designed for delivery in a primary care setting and as such is a suitable platform for use in outpatient clinical trials assessing new medications for alcohol¹³⁵¹³⁷. Primary goals include promoting compliance via psycho-educational methods as well as encouraging participation into self-help programs aimed at women¹³⁴. The initial session will be 3045 minutes followed by 10 minute follow-up sessions once per week. In addition, all subjects will receive CM providing participants with the opportunity to increase chances of winning variable dollar prizes at study completion for kept appointments. See Human Studies Section for full details of gender-specific recruitment goals (1.2) & CM protocol (4.1.3). **3.5.3 Outpatient Assessments:** Primary Outcomes: All participants will be required to provide a urine and breathalyzer screen at each appointment. In addition, the Time-Line Follow-Back Interview¹³⁰ will be used to assess all alcohol and nicotine use in the previous 90 days at baseline and weekly during the 10 week treatment trial. Primary alcohol use outcomes will be: (1) time to initial drink and heavy drinking (men: ≥ 5 drinks; women: ≥ 4); (2) frequency: the total number of days of alcohol use; and (3) quantity: the average amount of alcohol use (no. of drinks) per occasion. Subjects will be considered drop-outs if they receive two phone calls and two letters inviting them to return. We will attempt to assess these early terminators at the time of discontinuation, at the 10 week termination point, and at the follow-up period. These women will be withdrawn from the study but considered in the intent-to-treat efficacy analyses. Secondary Outcomes: The following measures will be administered upon admission and twice weekly to assess the effects of GXR on craving, anxiety, mood, stress and regulation: AUQ; STAI; BDI; POMS-Bi; PSS; DERS; BIS-11 and Stroop. Data Safety: The following measures will be assessed: (i) Sitting and standing vital signs: every 15 minutes for one hour (ii) Liver function tests, glucose and Complete Blood Count (CBC): weeks 4 and 8 for abnormal values (iii) Systematic Assessment of Treatment Emergent Events (SAFTEE): every week to assesses the severity and duration of potential physical or health problems. Adverse events will be documented according to the criteria outlined in the Human Subjects section 6.0. (iv) Blood draw to assess

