Data Analyses Plan: Aim1: To evaluate the safety and tolerability of GXR (3mgs/day) in women with AUD. All potential adverse effects from both treatment groups will be recorded twice weekly and classified, per body system and reaction, in a frequency table. Comparisons between treatment groups will be conducted using t-tests, chi-square tests and ANOVAs as appropriate (H1a). Aim2: To determine the preliminary efficacy of 10-week GXR (3mgs/day) versus PLA treatment on outcome measures in women with AUD: All analyses will be conducted using the intent-to-treat sample, and survival analyses will be used to examine medication effects on time to relapse measures. In order to model time intervals between events, reoccurring event-time analysis will be performed ¹³⁹. Hierarchical Linear Models (HLM) will be used to determine the effects of medication on continuous dependent variables, including % days abstinent and number of days in treatment (H2a), as well as secondary outcome variables, including craving, stress, anxiety, mood (H2b). Failures in treatment attendance will be accounted for by treating time as a random effect. Aim 3: To better determine the mechanisms underlying efficacy, by conducting a parallel laboratory study: Linear Mixed Effects (LME) models will examine the effects of medication on all Dependent Variables following stress versus neutral imagery within the laboratory (H3a). In order to elucidate the contribution of GXRrelated stress system changes in

the laboratory on primary drinking outcomes, correlational, regression and survival analyses will be performed as appropriate (H3b).

FUNDING STATUS, DETAILS

NIAAA have stated that they are in the process of issuing a restricted NOA, pending IRB approval.

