Guanfacine extended release (GXR) treatment: GRX (Intuniv; manufactured by Shire) is an alpha2-adrenergic agonist that is known to preferentially bind to alpha-2A-adrenergic receptors which are highly concentrated in the prefrontal cortical regions 148. While initial reactions to Guanfacine are common, most symptoms are mild and include fatigue, sedation, light-headedness, dizziness and vertigo, and tend to disappear either on continued dosing or following dose adjustment 18, 149. In fact, one major advantage of Guanfacine over other alpha2 adrenergic agonists such as clonidine, is that it is less sedating with less hypotensive potential in both children and adults 73, 75, 111-113. No serious side effects have been noted in adult populations, between the ages 18-65 and there are no reported differences in responses between elderly and younger populations. The most serious side effect in pediatric patients are reports of mania and aggressive behavior in pediatric subjects with ADHD 150. This side effect has not been documented within adult populations and there is no evidence that Guanfacine will pose a greater risk to the proposed study sample than those seen in children and adults with ADHD. One potential risk of study participation, however, is that GXR may result in series adverse effects. As such, we have ensured that important precautions are in place to minimize this risk: **(a)** the dosing levels of GXR (3mgs) is within the range safely used in outpatient studies comprising children and adults with ADHD and tic disorders, commonly ranging from 1.5 to 4 mg/day 73, 75, 149. Moreover, our prior published and pilot data using immediate release Guanfacine indicates that doses of 3mgs are well tolerated in substance and alcohol abusing men and women 18, 92. **(b)** Participants' heart rate, blood pressure and self-reports of any potential adverse effects are monitored twice weekly while taking part in outpatient treatment **(c)** As this study represents a preliminary outpatient trial in women with AUD, we propose a longer than standard "lead in" phase of 21 days. Other outpatient studies recruiting young adults and administering higher doses, have employed 16-day titration phases 118.

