Aim1: To evaluate the safety and tolerability of GXR (3mgs/day) in women with Alcohol Use Disorder (AUD). All potential adverse effects from both treatment groups were recorded twice weekly and classified. Descriptive statistics are displayed in a frequency table.

Aim2: To determine the preliminary efficacy of 10-week GXR (3mgs/day) versus PBO treatment on outcome measures in women with AUD: Linear Mixed Effects (LMEs) models were used to analyze data from the intent-to-treat sample where, for all Dependent Variables (% no. of heavy drinking days, % no. of days abstinent, % drinks consumed on any one occasion, alcohol craving, depressive symptomatology, anxiety and emotion regulation), the Between Group Factors of Group (GXR, PBO) and Within Group Factors of Time-points (12-weeks), represented the Fixed Effects and Subjects represented the Random Effects. Demographic and drug use variables differing between Treatment Groups and associated with the Dependent Variables were entered as covariates into the models and a Compound Symmetry covariance structure was applied to the model. Descriptive statistics were additionally conducted on % no. of negative urines collected across the trial.

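### Outpatient sitting and standing blood pressure and heart rate are collected as safety data, but SAP Aim 1 plans no analysis of them, so a group-level fall on GXR could go unreported

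*Combined protocol and SAP*

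**What the plan says.** **Collection.** The Data Safety part of protocol section 3.5.3 (Outpatient Assessments) lists first "Sitting and standing vital signs: every 15 minutes for one hour". The weekly assessment list for the virtual visits includes "Vitals – sitting to standing". The GXR paragraph under Risk to Subjects gives twice-weekly heart rate and blood pressure monitoring as a precaution against drug risk. The COVID-19 mailing package adds a "blood pressure heart rate daily log".

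**Analysis.** Protocol Aim 1 (STATISTICS, Data Analyses Plan) has adverse effects "classified, per body system and reaction, in a frequency table". It then provides for t-tests, chi-square tests and ANOVAs between arms where suitable, without naming a variable. SAP Aim 1 reads in full, after its title: "All potential adverse effects from both treatment groups were recorded twice weekly and classified. Descriptive statistics are displayed in a frequency table". The SAP Aim 2 dependent variables are drinking measures, craving, depressive symptoms, anxiety and emotion regulation; vital signs are not among them.

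**Expected effect.** Section 1.4.1 reports of the pilot: "At baseline, GUA reduced cardiovascular output in women compared with both PLA groups" (p<.0001). It adds that systolic pressure was attenuated in both sexes on guanfacine. Risk to Subjects names light-headedness and dizziness among the common reactions.

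**The concern.** H1 states that GXR will be safe and well tolerated in women with AUD. Lower blood pressure and pulse are the physiological effects that the documents themselves make most foreseeable, and the trial measures them repeatedly in both arms. If the SAP is followed as written, the safety results consist of an adverse-effect frequency table. A drop in mean pressure, or a larger sit-to-stand fall, spread over many women whose individual readings look ordinary would not show in that table. H1 would then be judged without an estimate of an effect that the data could supply.

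**Working it through.** The point is a missing analysis. The documents state no sample-size, power or precision figure for it, so there is no plan figure to reproduce. The check is to trace each route by which outpatient vital signs could reach the results.

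1. **SAP Aim 1.** Adverse effects only, descriptive only. It has no vital sign, change score, orthostatic measure or between-arm comparison.
2. **SAP Aim 2.** A mixed model on a closed list of outcomes, none of them a vital sign.
3. **Protocol Aim 1.** The t-tests and ANOVAs suit continuous data and could be stretched to cover vital signs. The text does not say so, and the SAP does not carry the comparisons forward.
4. **Protocol Aim 3.** A mixed model on the laboratory dependent variables, which include heart rate and blood pressure before and after imagery. It is a mechanism analysis, uses only women who reach week 10, does not use the outpatient sit/stand series, and has no SAP section.
5. **Adverse-event route.** Under Monitoring and reporting Adverse Events, an unwanted sign or a worsened abnormality counts as an AE. No numeric limit is given, and reported events count when staff judge them clinically important. Individual low readings can enter this way; a change in a group mean cannot.
6. **DSMB.** The quarterly review is described as a review of adverse event sheets.

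No route estimates the between-arm difference in the outpatient series.

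**Precision available if it were estimated (a guide only).** Inputs from the documents: 60 women in two arms, and up to 30% drop-out. Assumptions not in the documents: equal allocation, drop-out equal between arms, systolic SD of 10 to 15 mmHg, and correlation of 0.5 between intake and visit readings.

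- Women per arm: 60/2 = 30; after drop-out, 60 × 0.70 = 42, and 42/2 = 21.
- 95% CI half-width at one visit, adjusted for intake: t(0.975, 2n−2) × SD × √(1−ρ²) × √(2/n).
- n = 30: 2.002 × 0.866 × 0.258 × SD = 0.448 × SD, giving 4.5 mmHg (SD 10), 5.4 (SD 12) and 6.7 (SD 15).
- n = 21: 2.021 × 0.866 × 0.309 × SD = 0.540 × SD, giving 5.4, 6.5 and 8.1 mmHg.
- With ρ = 0, so that adjustment gains nothing, the factor 0.866 becomes 1. The ranges over SD 10 to 15 are then 5.2 to 7.8 mmHg at n = 30 and 6.2 to 9.4 mmHg at n = 21.

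A mixed model that averages over visits would narrow these intervals unless readings at different visits were perfectly correlated.

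**The case against.** The case for the plan has several sound parts.

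- **Low readings are not simply lost.** A reader might infer that a fall in pressure without symptoms would never be reported. The AE definition does not support that: an unwanted sign qualifies without symptoms. Dizziness and light-headedness are also sought weekly through the SAFTEE.
- **The protocol is not silent.** A reader might infer that neither document plans any between-arm safety comparison or any test of heart rate and blood pressure. Protocol Aim 1 does plan comparisons, though of unnamed variables, and protocol Aim 3 would model laboratory heart rate and blood pressure.
- **The evidence for a large effect is thin.** The pilot had 8 women among 24 participants and used immediate-release guanfacine. The risk section describes guanfacine as "less sedating with less hypotensive potential in both children and adults" relative to other drugs of its class. That is a reassurance, and the section also calls most symptoms mild. This is reason to estimate the effect under GXR, not to presume a large one.
- **A power contrast is not supported.** It is tempting to show that continuous readings have far more power than coded hypotension events. The documents give neither a blood-pressure effect nor event rates, and no link between the two, so such a contrast would rest on invented inputs.

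What survives is narrower: the outpatient series, designated as safety data, has no analysis in the SAP, and a group-level shift in it would not be seen.

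**Conclusion.** The gap is real and modest. The text shows plainly that no SAP analysis of the outpatient vital signs exists. That a material fall in pressure would go unreported is possible but not shown; it depends on an effect size that the documents do not give. The primary efficacy results are unaffected, but the Aim 1 conclusion is incomplete.

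Under the stated assumptions, with ρ = 0.5, the trial could place a 95% interval of about ±4.5 to ±6.7 mmHg around a single-visit systolic difference with all women present, or ±5.4 to ±8.1 mmHg after 30% drop-out. That is informative for a preliminary trial, though too wide to rule out small shifts. The week 4 and 8 liver function, glucose and blood count results, also listed under Data Safety, have the same gap.

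**What to change.** Add to SAP Aim 1:

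- A summary by arm and visit of sitting systolic and diastolic pressure, heart rate and sit-to-stand change. Give the GXR-minus-placebo difference and 95% CI from a mixed model adjusted for the intake value.
- A definition of that intake value. In the COVID-19 procedures, the Intake 2 sit/stand recording is described as taken at the end of the session, after the first dose, so the SAP should say which reading serves as baseline.
- A count by arm of women with any reading outside limits set by the study physician. These limits serve tabulation only and change nothing in participants' care.
- Week 4 and 8 liver, glucose and blood count values by arm, as shifts from baseline.

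The SAP is written in the past tense. If unblinding has already occurred, label these analyses and limits post hoc. The home log can be left out: it appears only in the COVID-19 mailing package, and its completeness is unknown.

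The cost is a short SAP addition and a little programming on data already scheduled for collection. The downside is a possibly less favourable safety section.

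### SAP Aim 2 omits, without a reason, the protocol's time-to-drinking analyses and its comparison of days in treatment, and does not carry over the primary and secondary labels

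*Combined protocol and SAP*

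**What the plan says.** Protocol, section 3.5.3 (Outpatient Assessments), numbers three primary alcohol outcomes. The first is introduced as "Primary alcohol use outcomes will be: (1) time to initial drink and heavy drinking", with heavy drinking set at four or more drinks for women. The second is "frequency: the total number of days of alcohol use". The third is "quantity: the average amount of alcohol use (no. of drinks) per occasion". The symptom scales come under a separate label: "Secondary Outcomes: The following measures will be administered upon admission and twice weekly to assess the effects of GXR on craving".

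Protocol, STATISTICS, Data Analyses Plan, Aim 2: "All analyses will be conducted using the intent-to-treat sample, and survival analyses will be used to examine medication effects on time to relapse measures". It adds a recurrent-event analysis, citing a paper on marginal regression for multivariate failure times (reference 139). Hierarchical linear models are planned for continuous outcomes. Under H2a these are % days abstinent and number of days in treatment; under H2b, labelled secondary, they include craving, stress, anxiety and mood.

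The protocol abstract describes the primary outcomes as abstinence and treatment adherence, under H2a.

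SAP, Aim 2, states one inferential method, linear mixed effects models in the intent-to-treat sample, "for all Dependent Variables (% no. of heavy drinking days, % no. of days abstinent, % drinks consumed on any one occasion". The list then continues with craving, depressive symptoms, anxiety and emotion regulation. The only other analysis is a descriptive summary of negative urines. The words primary and secondary do not appear, and no change from the protocol is acknowledged.

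**The concern.** A SAP normally turns the protocol's outcomes into models. Here the first-listed primary alcohol outcome and the retention half of H2a have no model. Two questions are at stake: whether GXR delays the first drink or first heavy drinking day, and whether it keeps women in treatment. The protocol intends the results to inform a larger Phase II trial, so losing either answer matters even though this trial is preliminary.

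Two drinking outcomes also change form without comment. Time to heavy drinking becomes a percentage of heavy drinking days. An average number of drinks becomes a percentage of drinks with nothing to say what it is a percentage of, so a second analyst could not compute it.

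Finally, the SAP does not say which of its seven variables are primary. The protocol does not settle this cleanly either, because the abstract and section 3.5.3 describe the primary set differently.

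**Working it through.** There is no sample-size or power figure to reproduce, and the point does not depend on one. The check sets the texts side by side.

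| Protocol outcome | Where it is primary | Protocol method | SAP Aim 2 |
|---|---|---|---|
| Time to first drink | 3.5.3, item 1 | Survival; recurrent events | Absent |
| Time to heavy drinking | 3.5.3, item 1 | Survival; recurrent events | Absent; % heavy drinking days instead |
| Days of alcohol use, or % days abstinent | 3.5.3, item 2; abstract (abstinence) | Hierarchical linear model (% days abstinent) | Present as % days abstinent |
| Average drinks per occasion | 3.5.3, item 3 | Not named individually | Present as an undefined percentage |
| Days in treatment | Abstract, H2a (adherence) | Hierarchical linear model | Absent |

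**Count.** In section 3.5.3, item 1 of 3 has no analysis in the SAP, in either of its two parts. Of the two H2a measures named in the Data Analyses Plan, 1 of 2 has none. Merging the lists gives 3 of 5 absent, but no section of the protocol lists five primaries. That count depends on splitting item 1, joining days of use with % days abstinent, and adding days in treatment from another section.

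**Does % days abstinent stand in for time to first drink?** No. Over the 10 weeks (70 days), a woman who drinks every day of the first half and one who drinks every day of the second half both score 35/70 = 50%. Their first drinks fall on day 1 and day 36. Modelling the percentage week by week does not fully cure this. A weekly group mean of 50% arises if every woman drinks on half the days, so that all have had the event. It also arises if half the women drink daily and half never do, so that half have had it.

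**Does any SAP variable stand in for retention?** No. All seven describe drinking or symptoms. None records how long a woman stayed.

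**Are the data there?** Yes. The timeline follow-back is taken "at baseline and weekly during the 10 week treatment trial", and kept appointments are tracked for contingency management. For women who drop out the protocol adds: "We will attempt to assess these early terminators at the time of discontinuation, at the 10 week termination point, and at the follow-up period".

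**Expected dropout.** Rationale / overview allows up to 30% of 60 women, 0.30 × 60 = 18, leaving 42 for the laboratory session. The Human Subjects paragraph under Study sample applies the same 30% but expects at least 49 AUD women. That implies 60 − 49 = 11 lost, or 18%. (49 is 70% of 70, the 60 AUD women plus the 10 nicotine-dependent women, but the text says AUD women.) The two figures conflict, so expected dropout is only loosely known. On either figure, retention is worth comparing between arms.

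**The case against.** **Silence is not withdrawal.** The SAP is attached to a protocol whose survival plan and outcome labels still stand. This is right, and it limits the point: the texts need reconciling. But the SAP says its models served all dependent variables and then lists them, which reads as complete.

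**% heavy drinking days is not foreign to the protocol.** Item 1 of section 3.5.3 already names heavy drinking and sets its threshold. That stands. A reader might infer a wholly new outcome; the documents show only a change of metric.

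**Time to first drink may say little.** Women may enter on a positive screen, so some may still be drinking. This could be a good reason for a change, but the SAP does not give it, and it does not explain dropping days in treatment.

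**The trial is preliminary.** True, and it is why formal multiplicity control is not the issue. It does not excuse an unexplained omission.

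A reader might also infer that seven unranked variables raise the false-positive risk above the protocol's, or that any of the seven could be presented as the main result. The documents support neither. They give no significance level. Setting the protocol's primaries alone against every SAP variable is not like for like: with the eight secondary measures of section 3.5.3, the protocol's merged list is 5 + 8 = 13 against the SAP's 7. The protocol's labels also remain in force.

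Nor does the SAP's past tense show that the changes followed unblinding. It leaves the timing unstated.

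**Conclusion.** The concern holds as a mismatch between protocol and SAP. Aim 2 of the SAP omits, without a reason, the time-to-event analyses of the first numbered primary alcohol outcome and the comparison of days in treatment under H2a. It also changes the metric for heavy drinking, leaves the drinks-per-occasion variable undefined, and does not carry over the outcome labels. If only the SAP's analyses are run, delay of drinking, delay of heavy drinking and retention are not tested. The conclusion rests on reading the SAP's variable list as complete, and on the absence of any gap or redaction mark in Aim 2 that would explain the omission. It does not rest on any assumed error rate, power, dropout figure or date of change.

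**What to change.** In SAP Aim 2:

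1. Restore the intent-to-treat survival analyses of time to first drink and to first heavy drinking day, and the recurrent-event analysis. State the time origin and censoring rule, which the protocol leaves open. Randomisation and the last timeline follow-back day are a reasonable option, with a sensitivity analysis for informative dropout. Note that time to first drink may carry little information in women still drinking at entry.
2. Restore the between-arm comparison of days in treatment. Each woman contributes one value, so a two-group or time-to-dropout comparison suits it better than the planned hierarchical model. Mark this as a change of method.
3. Carry the primary and secondary labels into the SAP, reconcile the abstract with section 3.5.3, and report the primaries as preliminary.
4. Use the protocol's average drinks per occasion. Label % heavy drinking days and every other departure as a change, with its date, its reason and whether it preceded unblinding.
5. If dropout is cited, reconcile the 42 and 49 women first.

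The cost is a few extra models on data already collected, plus a dated note of changes. A note cannot repair a change made after unblinding; a primary first named then would have to be reported as post hoc.
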